6. STUDY DRUGS

The following investigational drugs will be provided. Premedications or medications used to treat infusion-related reactions should be sourced by the investigative sites if available and permitted by local regulations.

Product Description	Potency	Packaging/Appearance	Storage Conditions (per label)
(Nivolumab) Solution for Injection	100 mg (10 mg/mL)	10 mL/vial (5 or 10 vials/carton)	Store at 2° - 8°C. Protect from light and freezing.
Ipilimumab Solution for Injection	200 mg (5 mg/mL)	40 mL/vial (4 vials/carton)	Store at 2°- 8°C. Protect from light and freezing.

An investigational product, also known as investigational medicinal product in some regions, is defined a pharmaceutical form of an active substance or placebo being tested or used as a reference in a clinical study, including products already with a marketing authorization but used or assembled (formulated or packaged) differently than the authorized form, or used for an unauthorized indication, or when used to gain further information about the authorized form.

The investigational product should be stored in a secure area according to local regulations. It is the responsibility of the investigator to ensure that investigational product is only dispensed to study subjects. The investigational product must be dispensed only from the official study site by authorized personnel according to local regulations.

6.1 Storage of Study Drug

The product storage manager should ensure that the study drug is stored in accordance with the environmental conditions (temperature, light, and humidity) as determined by BMS. If concerns

regarding the quality or appearance of the study drug arise, the study drug should not be dispensed and contact BMS immediately.

Study drug not supplied by BMS will be stored in accordance with the package insert. Investigational product documentation (whether supplied by BMS or not) must be maintained that includes all processes required to ensure drug is accurately administered. This includes documentation of drug storage, administration and, as applicable, storage temperatures, reconstitution, and use of required processes (e.g., required diluents, administration sets). Infusion-related supplies (e.g., IV bags, in-line filters, 0.9% sodium chloride injection, 5% dextrose injection) will not be supplied by the sponsor and should be purchased locally if permitted by local regulations.

Please refer to the current version of the Investigator Brochure (IB) and/or pharmacy reference sheets for complete storage, handling, dispensing, and infusion information for nivolumab and ipilimumab.

6.2 Concomitant medications

Permitted concomitant medications

Investigators may prescribe concomitant medications or treatments (e.g., acetaminophen, diphenhydramine) deemed necessary to provide adequate prophylactic or supportive care except for those medications identified as “excluded” as listed under Excluded Concomitant Medications.

Excluded Concomitant Medications

The following medications are considered exclusionary during the study.

1. Any investigational anticancer therapy other than the protocol specified therapies.
2. Any concurrent chemotherapy, radiotherapy (except palliative radiotherapy), immunotherapy, biologic or hormonal therapy for cancer treatment. Concurrent use of hormones for noncancer-related conditions (e.g., insulin for diabetes and hormone replacement therapy) is acceptable.
3. Immunosuppressive medications including, but not limited to systemic corticosteroids at doses not exceeding 10 mg/day of prednisone or equivalent, methotrexate, azathioprine, and TNF- α blockers. Use of immunosuppressive medications for the management of investigational product-related AEs or in subjects with contrast allergies is acceptable. In addition, use of inhaled and intranasal corticosteroids is permitted. A temporary period of

steroids will be allowed for different indications, at the discretion of the principal investigator (e.g., chronic obstructive pulmonary disease, radiation, nausea, etc.).

4. Live attenuated vaccines within 30 days of nivolumab and ipilimumab dosing (i.e., 30 days prior to the first dose, during treatment with nivolumab and ipilimumab for 30 days post discontinuation of nivolumab and ipilimumab). Inactivated vaccines, such as the injectable influenza vaccine, are permitted.

Table 2. Prohibited and Rescue Medications

Prohibited medication/class of drug:	Usage:
Additional investigational anticancer therapy concurrent with those under investigation in this study	Should not be given whilst the patient is on IP treatment
mAbs against CTLA-4, PD-1, or PD-L1	Should not be given whilst the patient is on IP treatment through 90 days after the last dose of IP
Any concurrent chemotherapy, local therapy (except palliative radiotherapy for non-target lesions, e.g., radiotherapy, surgery, radiofrequency ablation), biologic therapy, or hormonal therapy for cancer treatment	Should not be given whilst the patient is on IP treatment. (Concurrent use of hormones for non-cancer-related conditions [e.g., insulin for diabetes and hormone replacement therapy] is acceptable.)
Immunosuppressive medications, including, but not limited to, systemic corticosteroids at doses exceeding 10 mg/day of prednisone or its equivalent, methotrexate, azathioprine, and tumor necrosis factor α blockers	Should not be given whilst the patient is on IP treatment. (Use of immunosuppressive medications for the management of IP-related AEs or in patients with contrast allergies is acceptable. In addition, use of inhaled, topical, and intranasal corticosteroids is permitted.)
Live attenuated vaccines	Should not be given through 30 days after the last dose of IP during the study
VEGF inhibitors such as sunitinib, sorafenib and bevacizumab	Should not be given 90 days prior to first dose of investigational drug and with 30 days after last dose of investigational drug

Rescue/supportive medication/class of drug:	Usage:
Concomitant medications or treatments (e.g., acetaminophen or diphenhydramine) deemed necessary by the Investigator to provide adequate prophylactic or supportive care, except for those medications identified as “prohibited” as listed above	To be administered as prescribed by the Investigator
Best supportive care (including antibiotics, nutritional support, growth factor support, correction of metabolic disorders, optimal symptom control, and pain management [including palliative radiotherapy, etc.])	Should be used when necessary for all patients

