Study Design

This is a single arm, open label, prospective study evaluating the safety and clinical efficacy of the combination of nivolumab, ipilimumab and hypofractionated palliative radiation therapy (SBRT) in patients with advanced salivary gland cancer.

Patients enrolled will receive the following treatment (see Section 5.1.1):

1. Nivolumab 3mg/kg IV Q 2 weeks x 12 doses followed by Nivolumab 480 mg IV Q4 weeks x 8 doses
2. Ipilimumab 1 mg/kg IV Q6 weeks x 4 doses
3. Hypofractionated radiation therapy (SBRT) given to a total dose of 24Gy given in 3 fractions every other day over 1 week and initiated 2 weeks after the first dose of nivolumab and ipilimumab. The target lesion will be a local/regional or metastatic disease site that per the multidisciplinary head and neck team, requires local control for palliation and/or prevention of impending symptoms.

Both nivolumab and ipilimumab have well established toxicity profiles as a single agent and in combination. However, since the combination of nivolumab, ipilimumab and palliative radiation has not previously been described or studied, the first 6 patients who will be enrolled in this study will represent the initial safety run-in phase. Patients will receive full dose nivolumab and ipilimumab. Enrollment will be halted until these first 6 patients complete the first 12 weeks of treatment and acute toxicities will be reviewed. If more than 2 DLTs (to be defined in Section 5.1.2) are noted in this 6 patient cohort, a dose modification will be implemented (Section 5.1.1) for the remaining 14 patients who will be enrolled in the expansion cohort. Enrollment period is 24 months and duration of the trial 48 months.

Study Population

The study aims to enroll patients with salivary gland carcinomas (WHO, 2005), who are not candidates for curative intent therapy and who have a target lesion (either local/regional or distant metastatic site involving the lung and/or bone), that requires local control for palliation, as determined by a multidisciplinary team.

Inclusion Criteria:

1. Histologically proven salivary gland carcinoma (WHO, 2005) arising from a previous head and neck primary site, and located within the head and neck region, lung or bone, and who are not candidates for curative intent therapy.
2. ≥ 18 years old at the time of signing informed consent.

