16. Patient is ≥ 5 years free of another primary malignancy, except: a) if the other malignancy is basal cell carcinoma or cervical carcinoma in situ or b) if the other primary malignancy is not considered clinically significant and is requiring no active intervention

Exclusion Criteria:

The subject ***must be excluded*** from participating in the trial if the subject:

1. Is currently participating in or has participated in a study of an investigational agent or using an investigational device within 4 weeks of the first dose of treatment.
2. Has a target lesion/s for SBRT that demonstrate any of the following:
 - a. located within 2 cm of the proximal bronchial tree
 - b. > 5 cm (> 50 cc) in greatest dimension

3. Has a target lesion/s in a region that previously received high dose RT (>50 Gy) demonstrating any of the following:
 - a. carotid artery encasement (> 180 degrees)
 - b. unprotected carotid artery (i.e. skin is directly over the carotid without intervening soft tissue, especially after prior neck dissection without a vascularized free flap) (a&b due to risk of carotid blow out)
 - c. skin infiltration by tumor (due to risk of fistula)
 - d. located in the larynx/hypopharynx primaries (due airway threat)
 - e. treated with high dose radiation therapy (>50 Gy) within 6 months or less of trial enrollment
4. Prior receipt of an anti-PD-1, anti-PDL1 or anti-CTLA4 immune checkpoint inhibitor.
5. Current or prior use of immunosuppressive medication within 14 days before the first dose of nivolumab or ipilimumab. The following are exceptions to this criterion:
 - Intranasal, inhaled, topical steroids, or local steroid injections (e.g., intra articular injection)
 - Systemic corticosteroids at physiologic doses not to exceed 10 mg/day of prednisone or its equivalent
 - Steroids as premedication for hypersensitivity reactions (e.g., CT scan premedication)
6. Has received a prior monoclonal antibody within 4 weeks prior to study Day 1 or who has not recovered (i.e., \leq Grade 1 or at baseline) from adverse events due to agents administered more than 4 weeks earlier.
7. Has received prior chemotherapy, targeted small molecule therapy, or radiation therapy within 2 weeks prior to study Day 1 or who has not recovered (*i.e.*, \leq Grade 1 or at baseline) from adverse events due to a previously administered agent.
 - Note: Subjects with \leq Grade 2 neuropathy are an exception to this criterion and may qualify for the study.

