4.3 Efficacy Measurements

Adverse events will be monitored throughout the trial and graded in severity according to the guidelines outlined in the NCI Common Terminology Criteria for Adverse Events (CTCAE) version 5.0

Patients will be evaluated every 8 weeks (\pm 7 days) with radiographic imaging to assess response to treatment. CT or MRI will be used, per PI discretion, to scan areas of known disease. All imaging will be assessed using Response Evaluation Criteria in Solid Tumors (RECIST) 1.1 for determination of overall response rate (ORR) and progression-free survival (PFS).

4.4 Inclusion Criteria:

1. Histologically proven salivary gland carcinoma (WHO, 2005) arising from a previous head and neck primary site, and located within the head and neck region, lung or bone, and who are not candidates for curative intent therapy.
2. ≥ 18 years old at the time of signing informed consent.
3. Demonstrated disease progression during, or after discontinuation, of the most recent line of systemic therapy.
4. Have received any number lines of prior systemic therapy (including systemic therapy in the curative intent setting).
5. Have a target lesion/s deemed suitable by the treating physicians for SBRT with the intent of palliation or prevention of symptoms. This lesion must be:
 - a) 1-3 non-overlapping sites in the head and neck region OR
 - b) metastatic lesions outside the H&N region in the lung or bone (a minimum of 1 and a maximum 5 lesions will be irradiated), provided there is no significant overlap between the lesions.

Patients should have RECIST 1.1 criteria measurable disease in addition to the lesion/s treated with SBRT. If the site/s of SBRT were previously radiated to high dose RT (>50 Gy), there should be >6 month time interval between the last dose of radiation and the start of SBRT.

6. Have the ability to tolerate required SBRT-related procedures (e.g.: lie flat and hold position for treatment) as determined by the treating physician
7. Be willing and able to provide written informed consent for the trial and comply with the study visit requirements
8. Have measurable disease based on RECIST 1.1. (in addition to the lesion/s that will be treated with stereotactic radiation therapy)

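### Section 6.2 gives three palliative-radiotherapy rules that do not agree, and no endpoint rule covers a RECIST-measured lesion irradiated outside the study SBRT, so ORR and PFS can be biased upward.

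*Combined protocol and SAP*

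**What the plan says.** Three places in section 6.2 govern palliative radiotherapy while a patient is on study treatment:

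- **Excluded list, item 2:** "Any concurrent chemotherapy, radiotherapy (except palliative radiotherapy), immunotherapy, biologic or hormonal therapy for cancer treatment". The exemption has no limit on lesion. Surgery and ablation are not mentioned.
- **Table 2, prohibited row:** among the things not to be given on treatment is "local therapy (except palliative radiotherapy for non-target lesions, e.g., radiotherapy, surgery, radiofrequency ablation". Here the exemption is tied to non-target lesions.
- **Table 2, best-supportive-care row:** this lists "pain management [including palliative radiotherapy, etc", with the usage "Should be used when necessary for all patients". Again there is no limit on lesion.

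The term non-target appears only in that one row and is not defined. Elsewhere the protocol mostly uses target lesion for the lesion chosen for study SBRT. The synopsis (Study Design) says "The target lesion will be a local/regional or metastatic disease site that per the multidisciplinary head and neck team, requires local control for palliation". Exclusion criterion 2 begins "Has a target lesion/s for SBRT that demonstrate any of the following", and section 4.4, item 5, begins "Have a target lesion/s deemed suitable by the treating physicians for SBRT".

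The disease measured for response is separate. Inclusion items 5 and 8 require RECIST 1.1 measurable disease over and above the SBRT lesions. Section 4.3 schedules imaging every 8 weeks and assesses all of it by RECIST 1.1 for response and PFS. Statistical Considerations repeats RECIST 1.1 for response, counts PFS from enrollment and estimates it by Kaplan-Meier.

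**The concern.** Requiring measurable disease apart from the SBRT lesions keeps some disease outside the study radiation field, so that response can be read there. The Introduction's appeal to the abscopal effect depends on exactly that disease. If a measured lesion later receives palliative radiotherapy, its shrinkage reflects local treatment as well as the regimen. A growing lesion irradiated before its next scan may also fail to register as progression. Nothing in the plan separates these cases from true response or true disease control.

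The situation is plausible in this population. Patients have incurable disease and enter with at least one lesion that needs palliation. Under section 5.1.3.3, progression ends treatment only once it is confirmed and the investigator judges that benefit has ceased, so a patient with a growing lesion may stay on treatment. At stake are the two secondary efficacy endpoints.

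**Working it through.** No stated figure in the plan depends on this point, so the check is a comparison of texts followed by a note on scale. *Off-protocol* below means any local therapy beyond the study SBRT, whether or not section 6.2 permits it.

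**1. Do the three rules agree?** Take a measurable lesion outside the SBRT field.

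| Rule | May it receive palliative radiotherapy on treatment? |
|---|---|
| Item 2 | Yes |
| Table 2, best-supportive-care row | Yes, when necessary |
| Table 2, prohibited row, if non-target means not chosen for SBRT | Yes |
| Table 2, prohibited row, if non-target has a RECIST sense and the lesion is a RECIST target | No |

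No order of precedence is given. For an SBRT lesion needing further palliation, the first reading of the prohibited row also departs from the other two rules. So the rules disagree for some lesion on either reading.

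**2. Does the endpoint consequence need a particular meaning of non-target?** No. Item 2 and the best-supportive-care row each permit irradiation of a measured lesion by themselves.

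**3. Would the plan still score that lesion?** Yes. Section 4.3 applies RECIST 1.1 to all imaging. Neither it nor Statistical Considerations has a non-evaluability rule, a censoring rule or a sensitivity analysis for a measured lesion given local therapy.

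**4. Does the new-anti-cancer-therapy rule close the gap?** The section 7 footnotes and section 7.1.1.5 move a patient who starts new anti-cancer therapy to survival follow-up. They do not say whether palliative radiotherapy counts, and the review in 7.1.1.5 covers therapy begun after the last study dose. If radiotherapy does not count, scans continue and are scored. If it does, the patient moves to visits for which section 7.1.4.6 lists no imaging, and the handling of PFS is unstated.

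**5. Is the treatment recorded?** Concomitant medications are reviewed at visits. No section expressly asks for the date, site and dose of added radiotherapy.

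**6. Scale.** The input is N = 20 (synopsis; section 4.1).

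- One affected response: 1/20 = 0.05, or 5 percentage points of ORR.
- Exact 95% limits for x/n are the Beta(x, n−x+1) quantile at 0.025 and the Beta(x+1, n−x) quantile at 0.975. For 2/20 = 10% they are 1.2% to 31.7%; for 3/20 = 15%, 3.2% to 37.9%.
- The 10% starting point is only an illustration. It matches the approximate pembrolizumab response rate cited in the Introduction.

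**The case against.** **The rules may differ only in detail.** Item 2 is a short list entry, and Table 2 may simply refine it. Item 2's silence on surgery and ablation is an omission, not a contradiction. Its palliative radiotherapy could even mean the study SBRT, which the protocol also calls palliative. These arguments soften item 2. They do not dispose of the best-supportive-care row, which cannot be read as study SBRT and, unlike the rescue row before it, does not defer to the prohibited list.

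**Non-target may be meant in the RECIST sense.** This stands as a possibility. A reader might infer the opposite: that the protocol's SBRT usage settles the meaning, so that even the stricter row permits irradiating measured lesions. The documents do not support that as fact. Table 2 gives no definition, response is assessed by RECIST 1.1, synopsis inclusion item 5 omits the word target, and section 5.2 calls the irradiated lesion the index lesion. It can be said against the SBRT sense that it would bar the study's own radiation. But Table 2 also bars antibodies against CTLA-4 and PD-1, the class of the study drugs, so it evidently governs treatment beyond the protocol. Neither argument decides the meaning.

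**The consequence is limited.** This stands too. ORR and PFS are secondary and descriptive, with no efficacy threshold, and the sample size rests on toxicity. The intervals for 2/20 and 3/20 overlap widely. Study SBRT already treats lesions needing palliation, which may reduce early need for more.

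**Conclusion.** The point holds. The three passages need reconciling, non-target needs a definition, and the endpoints need a rule for measured lesions given off-protocol local therapy. As written, such lesions can be irradiated under two of the three rules and still be scored, and the likely direction is upward for both ORR and PFS.

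The size cannot be estimated, because the documents give no frequency of off-protocol radiotherapy. The one firm figure is 5 percentage points of ORR per affected response. It assumes that the irradiated lesion's shrinkage is enough to turn the patient's overall assessment into a response.

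A reader might go further in two ways:

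- **Projecting an inflated ORR, or setting an 8-week scan interval against the cited median PFS of 5 to 6 months.** The number of affected patients would be assumed. One patient's delayed progression date is also not a shift in the median, which it may leave unchanged.
- **Extending the point to the primary safety endpoint.** Extra radiation could complicate attribution. But section 5.1.2 already excludes from the DLT definition toxicity clearly due to another cause, and nothing in the documents shows how often attribution would be in doubt.

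**What to change.** 1. Reconcile section 6.2 item 2 and both Table 2 rows into one statement, including the status of surgery and ablation, which now sit inside the exception bracket. This review takes no view on which radiotherapy rule is right.
2. Use two separate terms throughout, *SBRT lesion* and *RECIST target lesion*.
3. State in the section 7 footnotes and section 7.1.1.5 whether off-protocol palliative radiotherapy counts as new anti-cancer therapy. If it does, state how PFS is then handled.
4. Record the date, site and dose of any off-protocol local therapy.
5. In section 4.3 and Statistical Considerations, count CR or PR only if documented before such therapy to a RECIST target lesion.
6. Add a PFS sensitivity analysis that treats such therapy as an event on its start date.

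Items 5 and 6 concern how outcomes are counted and restrict no patient's palliation. Other counting conventions are possible; what matters is that one is fixed in advance.

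The cost is wording changes in a few places, one CRF field and one extra analysis. The ORR may be slightly less favourable, because responses first documented after such therapy would not count.

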7. SCHEDULE OF ASSESSMENTS

Assessments to be performed at the times stipulated in the table and as clinically required in the management of the subject	Screening	all assessments to be performed pre-infusion unless stated otherwise						Safety Follow-Up ⁿ	Long-Term Follow-Up ^o	Survival Follow-Up ^p
		Weeks 1-6			Weeks 7-24	Weeks 25-52	End of treatment			
Day	- 28 to - 1	Day 1 of the Week (-2/+3)			-2/+3	-2/+3		-30	±14	±14
Week	-4 to -1	Week1	Week3	Week5					Q8 wks	Q12 wks
Written informed consent	X									
Demography and history of tobacco and alcohol use	X									
Previous treatments for head and neck cancer	X									
Tumor tissue sample	X									
Formal verification of eligibility criteria	X									
Medical and surgical history	X									
Urine hCG or serum βhCG ^a	X									
Physical examination ^b	X	X	X	X	X	X	X	X		
Vital signs ^c	X	X	X	X	X	X	X	X		
Weight ^c	X	X	X	X	X	X	X	X		

Clinical Study Protocol RG1718030 Drug Substance: Nivolumab and Ipilimumab IND Number: 140818 Protocol version 3.0 April 17, 2019	Assessments to be performed at the times stipulated in the table and as clinically required in the management of the subject	all assessments to be performed pre-infusion unless stated otherwise						Safety Follow-Up ⁿ	Long-Term Follow-Up ^o	Survival Follow-Up ^p
Screening	Weeks 1-6			Weeks 7-24	Weeks 25-52	End of treatment				
Day	- 28 to - 1	Day 1 of the Week (-2/+3)			-2/+3	-2/+3		-30	±14	±14
Week	-4 to -1	Week1	Week3	Week5					Q8 wks	Q12 wks
Nivolumab administration		X ^d	X ^d	X ^d	X ^d	X ^e				
Ipilimumab administration		X			X ^f					
Adverse event/serious adverse event assessment and concomitant medications ^c	X	X	X	X	X	X	X	X	X	X
Radiation therapy evaluation and radiation planning/simulation	X									
Palliative hypofractionated Radiation therapy			X ^g							
ECOG performance status ^c	X	X	X	X	X	X	X	X	X	
TSH with reflexive free T4 ^h	X	Repeat every 12 weeks								
Complete blood count ⁱ	X	X	X	X	X	X				
Serum chemistry ⁱ	X	X	X	X	X	X				
Urinalysis ^j	X	Additional testing as clinically indicated								
Coagulation parameters ^k	X	Additional testing as clinically indicated								
Correlative blood samples ^l	X			X						
Tumor assessments ^m	X			X	X			X		
Survival Status										X

^a Pre-menopausal female subjects of childbearing potential only

^b Full physical examination at screening and baseline; targeted physical examination prior to each administration of investigational drug, discontinuation of treatment and safety follow-up

^c To be done on each visit prior to administration of investigational drug. Concomitant medication collected up to the Safety Follow (-30 days post last dose of study treatment) or initiation of new anti-cancer treatment. AEs will be collected up to 100 days post last dose of study treatment or initiation of new anti-cancer treatment.

^d On weeks 1-24, see Section 5.1.1 for Nivolumab administration (-2/+3days), **nivolumab doses are given at least 12 days apart**

^e On weeks 25-52, see Section 5.1.1 for Nivolumab administration(-2/+3days) at a flat dose of 480mg, **nivolumab doses are given at least 12 days apart**

^f On weeks 1-24, see Section 5.1.1 for Ipilimumab administration(-2/+3 days) for 3 doses

^g XRT to begin 2 weeks after the first dose of Nivolumab and Ipilimumab and to be completed in 2 weeks

^h Add free T4 if TSH is abnormal. Repeat at least every 12 weeks.

ⁱ If screening laboratory assessments are performed within 3 days prior to Day 1 they do not need to be repeated at Day 1. Results for safety blood test must be available and reviewed before commencing an infusion. **During weeks 7-24:** CBC and serum chemistries will be done every 2 weeks prior to the nivolumab or nivolumab/ipilimumab infusions. **During weeks 25-52:** CBC and serum chemistries will be performed every 4 weeks prior to each nivolumab infusion.

^j Urinalysis performed at Screening and then as clinically indicated.

^k Coagulation tests: prothrombin time, aPTT and INR – only performed at Screening and then as clinically indicated.

^l Correlative blood samples will be collected on 3 occasions, prior to week 1, prior to week 8 and prior to week 16.

^m Timing of CT scans for tumor assessments will be every 8 weeks (+/- 7 days).

ⁿ If a subject initiates a new anti-cancer therapy within 30 days after the last dose of trial treatment, the 30 day Safety Follow-up visit must occur before the first dose of the new therapy. Once new anti-cancer therapy has been initiated the subject will move into survival follow-up.

^o Follow-up phase for patients that discontinue treatment for reasons other than disease progression (see Section 7.1.4.5).

^p Patients that have documented disease progression or starts treatment on new anti-cancer therapy will move into the survival follow-up phase.

